Specific Aim 1: To determine the effect of poor sleep efficiency on central nervous system (CNS) A β kinetics. Cognitively normal adults aged 45-65 with poor sleep efficiency of <85% measured by actigraphy (N=15) and good sleep efficiency of \geq 85% measured by actigraphy (N=15) will be compared. Sleep will be monitored with polysomnography (PSG) over 48 hours. CSF will be sampled via lumbar catheter every 2 hours. Each participant will be treated with placebo and infused with a stable isotope labeled amino acid for determination of CNS A β kinetics (e.g. production and clearance) and concentration.

Hypothesis 1: Cognitively normal adults with poor sleep efficiency will have increased A β production and concentration compared to cognitively normal adults with good sleep efficiency.

Specific Aim 2: To determine the effect of pharmacologic sleep induction on CNS A β kinetics in individuals with poor sleep efficiency. Participants from Aim 1 with poor sleep efficiency treated with placebo (N=15) will be compared to cognitively normal adults aged 45-65 with poor sleep efficiency treated with a dual orexin receptor antagonist (suvorexant) at 10 mg (N=15) and at 20 mg (N=15). CSF sampling frequency, sleep monitoring, and stable isotope labeled amino acid infusion for determination of CNS A β kinetics and concentration will be the same as in Aim 1.

Hypothesis 2: Sleep induction with suvorexant in participants with poor sleep efficiency will decrease A β production and concentration in a dose-dependent manner compared to placebo.

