A lumbar catheter and two IVs will be placed in the evening, with the goal of placement between 20:00-21:00, for collecting 6 ml of CSF every 2 hours for 36 hours (Figure 5) and 6ml of blood according to the specimen schedule (pg 7 of protocol). In order to efficiently use each participant's samples, each individual will also receive a placebo medication (for Specific Aim 2) and an infusion of ¹³C₆-leucine on Day 1 starting after catheter placement 0 (t=0) to label protein *in vivo* during intracellular translation in order to monitor A β kinetics (17, 40, 47). Participants will be allowed to sleep as they are able after receiving study medication (placebo or suvorexant). Nursing staff will use dim red lights (safelights) when collecting CSF and blood in the dark. The lumbar catheter ports will be placed on the outside of the gown sleeve for easy access to minimize disturbance during fluid collection. Participants will then sleep until final awakening in the morning.

During Day 2, all participants will be in well-lit rooms with regular monitoring for staying awake and naps will not be permitted. At 21:00 on Day 2 (t=24), all participants will follow the same sleep routine except that there will be no infusion of labeled ¹³C₆-leucine. All participants will again receive placebo for the second night. The IVs and lumbar catheters will be removed following the last CSF collection (t=36). Afterwards, participants will be monitored at the Clinical Research until discharge at approximately 17:00. A β kinetics will be quantified by mass spectrometry (MS).

Aim 2: To determine the effect of pharmacologic sleep induction on CNS A β kinetics in individuals with poor sleep efficiency

45 participants with sleep efficiency <85% measured by actigraphy will be admitted to the CRU in the afternoon (Day 1). All participants will have their sleep monitored with PSG throughout the study as described in Aim 1. A lumbar catheter and two IVs will be placed in the evening, with the goal of placement between 20:00-21:00, for collecting 6 ml of CSF and 6 ml of blood according to the specimen schedule (pg 7 of protocol). Following catheter placement on Day 1 (t=0), all participants will start an infusion of labeled ¹³C₆-leucine to label proteins *in vivo* during intracellular translation in order to monitor A β kinetics (17, 40, 47).

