Statistical Analysis and Power Calculation: All participants will be screened to determine if they have good or poor sleep efficiency as described above. 15 participants with good sleep efficiency will be treated with placebo (Aim 1). 45 participants with poor sleep efficiency will be randomized to either placebo (N=15) (Aim 1) or suvorexant 10 mg (N=15) or suvorexant 20 mg (N=15) (Aim 2). Change in CNS A β 40 and A β 42 production, clearance, and concentration in placebo-treated participants with poor sleep efficiency will be compared to placebo-treated participants with good sleep efficiency (Aim 1) and individuals with poor sleep efficiency treated with suvorexant (Aim 2) using a repeated measures analysis of variance (RM ANOVA), or repeated measures analysis of covariance (RM ANOCOVA) when covariates such as age are included in the analysis (49). Correction for multiple comparisons will be performed. A main question is whether the production rate of CSF A β during the production phase differs between subjects with good or poor sleep efficiency, or treated with drug, that will be statistically tested by appropriate interactions between subjects groups and time in the RM ANOCOVA. The average concentration of CSF A β over the entire time course during the sleep period will be tested by the main effects of subjects' groups, adjusting for the possible effects of age. Other parametric mixed effects models incorporating the typical sinusoidal profile over time will also be considered in the analyses. These analyses will be implemented by PROC MIXED/SAS or SPSS (50).

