To determine the sample size, I performed an *a priori* calculation with two-tailed t-tests to detect a difference between two independent means (two groups) for the number of subjects needed to find a difference in the AUC for both A β 40 and A β 42 during the 10-hour sleep period. With the preliminary data for control (good and poor sleep efficiency) and all sleep-induced participants, the mean and standard deviation of A β 40 and A β 42 AUCs (pM*hr) during the 10-hour period from 23:00-09:00 were used for the power calculation (see Table 1: “Control – Poor Sleepers (N=4)”, “Control – Good Sleepers (N=3)”, and “Sleep-Induced (N=8)”). We will be able to detect similar pM*hr differences as from the preliminary data between all groups and all A β isoforms with 13 participants in each group (effect size d range=1.17-1.57, $\alpha = 0.05$, Power $(1-\beta) = 0.8$), therefore this study is adequately powered with 15 participants in each group.

Alternative Approaches: We chose serial CSF collection via lumbar catheterization for the experimental approach because it provides the most detailed measures of A β kinetics and concentrations. An alternative approach could be to perform $^{13}\text{C}_6$ -leucine labeling with one lumbar puncture performed after the sleep period; differences in A β kinetics could be inferred by percent labeling of A β . However, with this approach the time relative to each participant's final awakening may be variable for each participant (e.g. 08:00 vs. 09:00) and does not easily account for different sleep start times. A larger sample size may also be required with this approach. Other potential problems for this study include participant recruitment and study completion. This study is intensive for participants. However, our preliminary study is similarly intensive and we have been able to achieve participant recruitment and completion goals. Screening participants by good and poor sleep efficiency may be more difficult than anticipated because participants will initially be referred from the community-based participant registry, Volunteers for Health, based on self-report and questionnaires. These measures may not correlate with the sleep efficiency found by actigraphy. If this occurs, we will need to screen more participants than

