For Aim 1, we will enroll two groups: 15 participants with good sleep quality (sleep efficiency by actigraphy $\geq 85\%$) and 15 participants with poor sleep quality (sleep efficiency by actigraphy $< 85\%$). All participants in Aim 1 will receive a placebo generated by the investigational pharmacy at Barnes-Jewish Hospital. For Aim 2, an additional 30 participants with poor sleep quality (sleep efficiency by actigraphy $< 85\%$) will be recruited and will receive either suvorexant 10 mg or suvorexant 20 mg, a dual orexin receptor antagonist approved by the Food and Drug Administration (FDA) for the treatment of insomnia (approved doses 5-20 mg). This group will be compared to the 15 participants with poor sleep quality in Aim 1 who received placebo. Participants who have poor sleep efficiency will be randomized to either placebo or suvorexant. There will be a total of 60 participants who complete the study.

Sampling plan and justification:

- Power calculations in the “Statistical Analysis and Power Calculation” portion of the research plan were based on preliminary data about the area under the curve differences in A β during a 10-hour sleep period (23:00-09:00) in participants with different sleep efficiency. Due to concerns about recruitment if participants have to repeat the study, the study power calculation is based on each participant completing the study once without repeating. 15 participants are required for each study arm (total N=60).
- Children will be excluded and age range will be limited to 45-65, as detailed in the previous section “Subject population characteristics”.

Vulnerable populations: We will not enroll participants from vulnerable populations.

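### Does testing the Aβ production rate through a group-by-time interaction, with the response and hours left unstated, call for a change to the plan?

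*Combined protocol and SAP*

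**What the plan says.** Production and concentration are the two outcomes in both hypotheses. Hypothesis 1 begins "Cognitively normal adults with poor sleep efficiency will have increased" and names production first.

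The Statistical Analysis and Power Calculation section lists production, clearance and concentration of Aβ40 and Aβ42 as outcomes for a repeated measures ANOVA, or ANCOVA with covariates such as age. It separates two tests:

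- **Production:** whether the rate "during the production phase differs between subjects with good or poor sleep efficiency", or with drug, "will be statistically tested by appropriate interactions between subjects groups and time in the RM ANOCOVA".
- **Concentration:** the average over the sleep period, tested by the main effect of group.

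On multiplicity it says "Correction for multiple comparisons will be performed". Mixed models with a sinusoidal time profile may also be considered.

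On sample size, the same section seeks the "number of subjects needed to find a difference in the AUC" for both isoforms over ten hours and concludes "therefore this study is adequately powered with 15 participants in each group".

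The Data and Safety Monitoring Plan adds that the labelling data will be fitted blinded with a compartmental model in SAAM II, and that comparisons are pre-specified. Sources of Materials gives CSF sampling every 2 hours from hour 0 to hour 36.

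**The concern.** A main question should have a test that a second analyst could reproduce, and the visible wording allows several.

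- **One value per participant.** Label is given on the first night only; on the second, "all participants will follow the same sleep routine except that there will be no infusion of labeled" leucine. The sampling justification adds that "the study power calculation is based on each participant completing the study once without repeating". A compartmental fit would ordinarily return one production rate per person, which leaves no time factor to interact with group.
- **A time series.** A group-by-time interaction can then respond to a difference in labelling delay or clearance even when production is equal.
- **The labelled fraction.** In a one-pool steady state, production cancels out of the slope, so a real production difference could be missed and a clearance difference reported in its place.

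The adequacy statement also covers the whole study, although only a concentration AUC was sized. At stake is whether a significant interaction could be read as a production effect when it is not one.

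**Working it through.** **1. The plan's own figure.** Inputs from the Statistical Analysis and Power Calculation section: two-sided t-test, α = 0.05, power 0.80, d from 1.17 to 1.57, 13 per group needed, 15 planned. The noncentrality is d × √(n/2).

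- n = 13, d = 1.17: 1.17 × √6.5 = 2.98, 24 df, critical t 2.064, power 0.816. The 13 reproduces.
- n = 15, d = 1.17: 1.17 × √7.5 = 3.20, 28 df, critical t 2.048, power 0.871.
- n = 15, 80% power: d = 1.06, since 1.06 × √7.5 = 2.90 gives power 0.800. If α is halved for two comparisons (an assumption, because the correction method is not stated), d = 1.18.

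For one production value per participant, the detectable d of 1.06 lies below the plan's smallest AUC effect. The documents give no production mean or SD, so neither adequacy nor shortfall can be shown for production.

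**2. Does a delay difference mimic a production difference?** The documents give no delay or rate variance, so every input here is assumed. The model is y = rate × max(0, t − delay) + noise, sampled every 2 h from 0 to 12 h, with 15 per group. Mean rate is 1 per h in both groups and mean delay 3 h. Rate CV is 15% or 30%, delay SD 0.5 or 1 h, and noise SD 0.3 or 0.6 with AR(1) correlation 0.5, giving eight settings. Ranges are rejection rates at nominal 5%, with a group difference in delay and equal production:

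| Test | Hours | 0.5 h difference | 1 h difference |
|---|---|---|---|
| Interaction, time as a factor (Greenhouse-Geisser) | 0-12 | 7.2-17.4% | 17.4-65.3% |
| Slope, time continuous | 0-12 | 6.9-14.6% | 16.2-49.1% |
| Interaction, time as a factor (Greenhouse-Geisser) | 6-12 | 4.2-5.8% | 4.5-5.9% |
| Slope, time continuous | 6-12 | 4.5-5.2% | 4.7-5.3% |

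(6,000 runs per cell; 1,500 for the third row.) Both codings inflate over 0-12 h and both are nominal over 6-12 h. The cause is the inclusion of samples taken before the rise, not the coding of time. A production phase that starts after the delay excludes those samples.

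**3. Does the choice of response matter?** Assume one pool at steady state: concentration C = P/k, labelled fraction f with df/dt = k(e − f), constant precursor enrichment e, and a 3 h delay. Then f = e(1 − exp(−k(t − 3))), which contains no P. Slopes over 6-12 h for k from 0.05 to 0.15 per h:

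- Production +30%: labelled-fraction slope 0%; labelled-concentration slope (f × C) +30%.
- k −30%: labelled-fraction slope −23.5% to −9.7%; labelled-concentration slope +9.2% to +29.0%.

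For example, the rise from 6 to 12 h at k = 0.10 is exp(−0.3) − exp(−0.9) = 0.334. At k = 0.07 it is exp(−0.21) − exp(−0.63) = 0.278. The ratio is 0.832, or −16.8%. Dividing by 0.7, because C rises as k falls, gives 1.188, or about +19%.

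The response therefore matters. The labelled fraction would be a poor stand-in for production under this model, but the plan does not name it as the response; it names production as the outcome and provides a compartmental model.

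**The case for a change.** The strongest case for a change is that a main question should not rest on the word appropriate. The possible readings are different tests, and one of them (a single fitted value) has no time dimension at all. The statement that comparisons are pre-specified does not supply the rule. Writing the rule down would cost only wording, and catheter failure, which Sources of Materials expects, may leave some participants with no rate.

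The description of the gap stands. What does not follow is that the plan leads to a wrong analysis:

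- The question is a rate within a named phase, so comparing slopes in that phase is the natural reading of the interaction, and it is valid for a response whose rise reflects production.
- If SAAM II returns one value per participant, an age-adjusted group comparison is the obvious analysis. The plan already lists production among the outcomes to be compared and allows age as a covariate.
- A tighter formula, such as turnover × mean concentration, is not clearly better. Its good behaviour was shown only on data generated from the one-pool steady-state model that it assumes, and the Background describes a diurnal concentration pattern that puts steady state in doubt.
- Figure 5 and the cited kinetic methods are not visible here and may define the timeline.
- The power paragraph and the sampling justification both tie the calculation to the 10-hour AUC. Alternative Approaches concedes the small preliminary numbers and plans an interim look at whether more participants are needed.

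Catheter failure is a separate missing-data matter and does not bear on the choice of test.

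**Conclusion.** No change to the plan is needed. The visible text omits the modelled response, the production-phase hours, the time coding and the link to the SAAM II output. These are definitions that analysts using this kinetic method would have to settle, and the plan's wording points them to a sensible choice. Harm appears only under readings that the plan does not adopt: the 17-65% rejection needs hours 0-12 and a 1 h shift in delay (1 to 2 SD of the assumed spread), and the labelled-fraction problem needs a response that is not named. Over hours 6-12 the interaction test holds its level.

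The broad adequacy sentence is loose, but the AUC figure beneath it is correct and no shortfall is shown for production. The conclusion rests on the production phase being taken to start after the labelling delay, and on the response being a fitted rate or a quantity whose rise reflects production. The rejection rates and slope changes depend on assumed kinetics and are illustrations, not estimates for this trial.

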45 participants will be randomized to receive a placebo, 10 mg of suvorexant, 20 mg of suvorexant during the CRU stay. Suvorexant is a dual orexin receptor antagonist that is approved by the Food and Drug Administration (FDA) for the treatment of insomnia. Suvorexant is also a drug with the same mechanism of action as was used in experiments to decrease A β with sleep in mice (8), therefore this will be a direct translation of this finding. Further, genetic manipulation of the orexin system to alter the sleep-wake cycle has been shown to drive A β pathology (51).

FDA-approved doses of suvorexant range from 5-20 mg. The drug's mechanism of action is to block orexin-A and orexin-B receptors. The orexin neuropeptide acts in the brain to promote wakefulness. Through antagonism of this system, sleep is induced. In a phase IIb randomized, double-blind, placebo-controlled study of patients with primary insomnia, suvorexant 10 mg increased sleep efficiency from 65.1% at baseline to 82.9% at night 1 and 84.4% at one month (48). Placebo-treated subjects increased sleep efficiency from 65.9% at baseline to 76.8% at night 1 and 77.8% at one month.

Participants will be allowed to sleep as they are able immediately with the lights turned off after medication dispensation (placebo or suvorexant). Nursing staff will use dim red lights (safelights) when collecting CSF and blood in the dark. The lumbar catheter ports will be placed on the outside of the gown sleeve for easy access to minimize disturbance during fluid collection. Participants will then sleep until final awakening the morning. During Day 2, all participants will be in well-lit rooms with regular monitoring for

staying awake and naps will not be permitted. On Day 2 ($t=24$), all participants will follow the same sleep routine except that there will be no infusion of labeled $^{13}\text{C}_6$ -leucine. Participants will receive the same placebo or suvorexant dose as the previous night (Figure 5). The IVs and lumbar catheters will be removed following the last CSF collection ($t=36$). Afterwards, participants will be monitored at the Clinical Research until discharge at approximately 17:00. A β kinetics will be quantified by MS.

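### Aim 2 concentration test: the plan does not commit to the hour-0 CSF value as a baseline covariate, a cheap optional gain in precision and not an error

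*Combined protocol and SAP*

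**What the plan says.** The relevant text is in Statistical Analysis and Power Calculation.

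- **Test for concentration.** The average level "over the entire time course during the sleep period will be tested by the main effects of" the groups, "adjusting for the possible effects of age".
- **Model.** Repeated measures ANOVA, or ANCOVA "when covariates such as age are included in the analysis". Other mixed models with a sinusoidal time profile may be considered.
- **Multiplicity.** "Correction for multiple comparisons will be performed", with no method or family named.
- **Power.** An unadjusted two-sample t-test on AUC, with "effect size d range=1.17-1.57" at alpha 0.05. The AUCs "during the 10-hour period from 23:00-09:00 were used for the power calculation". It gives 13 per group needed and 15 planned.

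Section B, Sources of Materials, lists CSF at hour 0 and every 2 hours to hour 36 for each participant, whatever the aim or group. It expects some catheters to fail. In the Aim 2 text, participants are randomised to placebo or one of two suvorexant doses and are dosed on both nights. No section names hour 0 as a covariate or defines an analysis baseline.

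**The concern.** A group main effect on an average level is judged against between-person variation. Any stable difference between people that an hour-0 sample could explain stays in the error term unless hour 0 is in the model. With 15 per arm, that may matter.

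The plan calls the study adequately powered at alpha 0.05 but also promises a multiplicity correction, which lowers the working alpha. Using a sample already scheduled could win back some of that loss. Leaving the covariate open also sits poorly with the Data and Safety Monitoring Plan, which says that comparisons are pre-specified.

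Two wording gaps bear on the same analysis. The plan does not say which night or nights form the sleep period, although there are two dosing nights. It also opens by speaking of change in concentration without saying change from what, and then tests and powers a level.

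**Working it through.** **Inputs from the plan.** 15 per arm, three randomised Aim 2 arms (N = 45), two-sided tests, d from 1.17 to 1.57, alpha 0.05.

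**Assumed.** The partial correlation r of hour 0 with the sleep-period average given age (not in the documents; 0 to 0.7 shown). A Bonferroni family of four tests, two doses by two isoforms, giving alpha 0.05/4 = 0.0125. Equal variance across arms.

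**1. The plan's own figure.** Two-sample noncentral t at d = 1.17, alpha 0.05: 13 per group gives power 0.816 and 12 gives 0.782, so the stated 13 reproduces. At 15 per group, power is 0.871.

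**2. Formula with covariates.** For N participants, k arms and c covariates:

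- degrees of freedom = N − k − c
- variance factor f = (1 − r²) × (N − k − 1)/(N − k − c − 1), with r = 0 for age only because d is in SD units given age
- noncentrality = d × √(7.5/f), where 7.5 = 15/2

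The plan describes one model across groups, so the error is pooled over the three Aim 2 arms.

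- Age only: df = 41, f = 41/40 = 1.025, noncentrality = 1.17 × √(7.5/1.025) = 3.17.
- Age plus hour 0: df = 40, f = (1 − r²) × 41/39. At r = 0.5, f = 0.75 × 1.051 = 0.788 and noncentrality = 3.61.

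**3. Power at d = 1.17, error pooled over three arms**

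| Model | alpha 0.05 | alpha 0.0125 |
|---|---|---|
| Age only | 0.871 | 0.708 |
| + hour 0, r = 0 | 0.862 | 0.693 |
| + hour 0, r = 0.2 | 0.875 | 0.715 |
| + hour 0, r = 0.3 | 0.892 | 0.742 |
| + hour 0, r = 0.5 | 0.941 | 0.834 |
| + hour 0, r = 0.7 | 0.99 | 0.956 |

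Break-even r is about 0.16 at both alphas.

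**4. Two-arm error instead.** Factors are 27/26 (df 27) for age only and (1 − r²) × 27/25 (df 26) with hour 0. At alpha 0.0125, power is 0.679 with age only and 0.655, 0.677, 0.705, 0.801, 0.940 over the same r values. Break-even is about 0.2.

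**5. Largest planned effect.** At d = 1.57 with age only and two-arm error, power is 0.982 at alpha 0.05 and 0.930 at 0.0125, so there is little to gain.

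**6. Missing hour-0 values.** Simulation (100,000 runs per setting, two-arm error, alpha 0.0125, d = 1.17) with two hour-0 values per arm missing at random and replaced by the mean pooled over arms gives 0.659, 0.675, 0.699, 0.780, 0.902. Age only gives 0.678 in the same simulation. Break-even stays near 0.2.

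**7. Simple change score.** If hour 0 and the average have equal variance, the variance factor (covariate-estimation terms aside) is 2(1 − r): 1.4, 1.0, 0.6 at r = 0.3, 0.5, 0.7. Adjustment gives 1 − r²: 0.91, 0.75, 0.51. A change score beats the unadjusted test only if r exceeds about 0.5, and adjustment does better at each of these values.

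**8. Clock mapping.** The Aim 1 text says "At 21:00 on Day 2 (t=24), all participants will follow the same sleep routine". Counting back, t = 0 is 21:00, so 23:00-09:00 is hours 2-12 on night 1 and hours 26-36 on night 2. Placement is targeted for 20:00-21:00, so the night-1 mapping may be off by up to an hour.

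**The case against.** The strongest reply is that nothing here is wrong. The sample size reproduces, the Aim 2 comparison is randomised, and the covariate wording is open enough to admit hour 0. All of that stands. A reader might infer that the test is biased without a baseline, or that the plan rules one out. The documents support neither reading; the gap is lack of commitment.

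The gain also cannot be sized from the documents. No r is given, it may be lower for night 2 than for night 1, and below break-even the covariate loses a little. That stands too, and is why a range is shown.

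A reader might infer that the trial is underpowered, at 68% or 71%. That rests on an assumed four-test Bonferroni family and on d = 1.17, which is the smallest effect over all groups and isoforms, including the Aim 1 contrast. The documents do not show that it is an Aim 2 effect.

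Nor should the figures be read as showing that age adjustment costs power. They hold d fixed in age-adjusted SD units. If d = 1.17 is in raw SD units, two-arm power at alpha 0.0125 is 70%, 73% or 77% for an assumed age-outcome correlation of 0.2, 0.3 or 0.4.

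Finally, change in concentration might already mean change from hour 0. That is possible, so the wording should be clarified and not simply replaced.

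**Conclusion.** The point holds as an optional improvement of low priority. For the randomised Aim 2 concentration analysis, the plan names only age and does not commit to a baseline value that is scheduled in everyone.

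If r is moderate (0.5), pooled-error power at d = 1.17 rises from 87% to 94% at alpha 0.05, and from 71% to 83% at alpha 0.0125. If r is near zero, 1 to 2 points are lost.

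This rests on the assumed r, the assumed multiplicity family, and hour 0 being drawn before the first dose. The order of events in the protocol suggests the last, but does not state it, and the sampling figure is not shown in the text reviewed.

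The point does not extend to production or clearance, because an unlabelled hour-0 sample gives no baseline for labelling kinetics. Nor does it extend to the main Aim 1 contrast. Those groups are not randomised and the hour-0 level may itself reflect sleep quality, so adjustment would change the question.

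**What to change.** Add to the analysis plan, for Aim 2 concentration only:

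1. Pre-specify the same-isoform hour-0 concentration as a covariate beside age or, equally sound, a constrained longitudinal model with a common hour-0 mean across arms. First confirm in the specimen schedule that hour 0 precedes the first dose.
2. State which night or nights, and which hours, form the sleep-period average, and keep hour 0 outside it. Do not use hour 24 as a baseline for night 2, because it follows the first night's dose.
3. Keep participants whose hour-0 value is missing. The constrained model does this directly; with the covariate, use the mean pooled over arms.
4. Say what change in concentration means. If change from hour 0 is intended, use hour-0 adjustment in place of a simple change score.
5. Leave the main Aim 1 contrast without hour-0 adjustment.

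The cost is a few sentences and one degree of freedom, with no new sample. If the sponsor prefers not to use hour 0, a sentence recording why would close the point.
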